	9	6-26 weeks	Fever (>38°C) - 1 Diarrhoea- 1	0 0	Serum antibody rise to vaccinees 2, placebo 0	
	42	6-26 weeks	Fever (>38°C) - 4 Diarrhoea- 2	5 1	Serum antibody rise to vaccinees 19, placebo 0	

SB Biologicals has acquired the strain and taken over the manufacturing process and clinical development of the 89-12 vaccine from AVANT and has implemented several process changes and prepared a lyophilized HRV vaccine based on a cloned P43 89-12 HRV strain (referred to as RIX4414).

It is known that the same vaccine can achieve different levels of immune response and efficacy in different study populations, and therefore it is important to test the study vaccine in different geographic settings. GSK Biologicals is therefore commencing trials in Asia, Latin-America and Africa to begin testing of its HRV vaccine's effectiveness in preventing gastroenteritis.

The aim of this dose-ranging study is to identify the most suitable dose and regimen of the vaccine for Bangladesh infants and to determine if there is a difference in immune responses between the two viral concentrations using two different schedules. The rationale for the use of several doses and several viral concentrations is four fold: First, to implement rotavirus vaccination as part of the existing EPI schedule, infants should be vaccinated at a very early age (6-8 weeks old) and with a short interval between doses. At this young age, infants are expected to have considerable levels of circulating maternal antibodies. The importance of maternally acquired anti-rotavirus specific antibodies has been evaluated in several clinical trials performed in infant-mother pairs. As expected, the presence of maternally acquired antibodies was shown to interfere with live attenuated oral rotavirus vaccine in infants (Pickering et al, 1995). The administration of an additional dose might overcome the potential interference of maternal antibodies. Therefore, the immunogenicity of GSK Biologicals' HRV vaccine needs to be evaluated at two and at three doses.

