- On day 42, insure that all concomitant medication taken during the study have been recorded.

Day 43 to 6 months.

- Monthly active surveillance to complete 6 months of followup. With each visit, inquire about symptoms or illnesses among subjects.
- At end of 6 months, terminate subject from the study

For infants(Part 2)

Day 0 (Visit 1)

- Same procedures as performed for toddlers in part 1.
- Obtain a blood sample for serology
- Prepare study vaccine and administer dose 1
- Collection of stool sample for rotavirus antigen by ELISA

Day 3, 7, 14, and 21 (first 150 subjects only)

- Collection of stool sample for rotavirus antigen by ELISA

Day 1-day 27

- Carry out active surveillance with all subjects by visiting house daily for 2 weeks and thereafter twice weekly. Measure rectal temperature daily. Use daily form to record symptoms or lack of symptoms. Have physician available at clinic and inform family of subjects that the physician is available should there be any illness during the time of the study. If subjects are brought to the clinic, record all symptoms in patient medical records. These medical records will be the source documents for the passive surveillance.

Day 28

- Insure that subject is eligible for dose 2 according to inclusion and exclusion criteria
- Obtain a serum blood sample for serology
- Prepare study vaccine and administer dose 2
- Collection of stool sample from subjects (first 150 only) for rotavirus antigen by ELISA

Day 29 – day 42

- Carry out active surveillance with all subjects by visiting house daily for 2 weeks. Measure rectal temperature daily. Use daily form to record symptoms or lack of symptoms. Have physician available at clinic and inform family of subjects that the physician is available should there be any illness during the time of the study. If subjects are brought to the clinic, record all symptoms in patient medical records. These medical records will be the source documents for the passive surveillance.

Day 31, 35, 42, 49 (first 150 subjects only)

- Collection of stool sample for rotavirus antigen by ELISA

Day 43-day 55

- Twice weekly active surveillance inquiring about symptoms or illnesses among subjects.

Day 56

- Insure that subject is eligible for dose 3 according to inclusion and exclusion criteria

- Obtain a serum blood sample for serology
 - Prepare study vaccine and administer dose 3
 - Collection of stool sample from subjects (first 150) for rotavirus antigen by ELISA
- Day 57-day 70

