Baseline characteristics of the subjects receiving vaccine and placebo will be examined for group comparability. Any significant baseline differences will be controlled for during data analysis. The frequency distribution will be examined to assess the distribution of data. Proportion of infants with adverse events will be compared between the different groups (vaccine, placebo, different doses and viral concentrations). Proportion of subjects that shed rotavirus at different time periods will be compared. Serological measures (proportion with ≥ 4 -fold increase in titer and geometric mean titer) will be compared between different viral concentrations/ doses and placebo recipients.

The proportions will be compared using χ^2 -tests and rate ratios (95% confidence intervals). The geometric mean titers (GMT) will be compared using non-parametric tests. Multivariate analysis will be done to simultaneously adjust for different factors.

Ethical Assurance for Protection of Human Rights

Describe in the space provided the justifications for conducting this research in human subjects. If the study needs observations on sick individuals, provide sufficient reasons for using them. Indicate how subject's rights are protected and if there is any benefit or risk to each subject of the study.

Human rotavirus vaccine (RIX4414), designed for preventing rotavirus will be evaluated among young children since the risk of the disease is greatest in that age group. Infants will be enrolled after their parents have been given a full explanation of the study and they have understood the implications of participating in this study, and have agreed to participate in writing. The study will be conducted according to Good Clinical Practices, the Declaration of Helsinki, and local rules and regulations of Bangladesh and the ICDDR,B.

The investigator and his staff will be aware of the possible increased risk of intussusception and will consider this diagnosis among children presenting symptoms of intussusception. The investigator and his staff will take appropriate actions to evaluate and treat the condition. A child with suspected intussusception will be referred to a local hospital in Dhaka (Children's hospital, Shishu Hospital). The hospital has the experience and capacity for diagnosis, non-surgical and surgical management of intussusception, and a pediatric surgeon at this hospital is a co-investigator on the protocol to assume

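### Baseline significance decides which covariates are adjusted for, and the titre comparison is stated as a test without a GMT ratio; the cost is precision and analyst discretion, not a shown rise in type I error

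*Protocol*

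**What the plan says.** The protocol's Data Analysis section starts with a comparability check: "Baseline characteristics of the subjects receiving vaccine and placebo will be examined for group comparability". The rule that follows is "Any significant baseline differences will be controlled for during data analysis". The section names no variable, test or threshold.

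For outcomes, it says "The proportions will be compared using" chi-square tests, with rate ratios and 95% confidence intervals. This covers the proportion of infants with at least a four-fold rise in titre. For titres it says only "The geometric mean titers (GMT) will be compared using non-parametric tests". It then adds "Multivariate analysis will be done to simultaneously adjust for different factors", without naming the outcome, the model or the factors.

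Two candidate covariates are known before any outcome is seen. Age at first dose runs from 6 to 14 weeks (inclusion criteria). The infant Day 0 visit includes the step "Obtain a blood sample for serology", and the Outline of the study confirms serum from all Part 2 subjects at each study visit. The Background section gives a reason to expect baseline immune status to matter: "the presence of maternally acquired antibodies was shown to interfere with live attenuated oral rotavirus vaccine in infants".

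**The concern.** Allocation follows a randomisation list prepared by the sponsor, so a significant baseline difference says nothing about whether the variable affects the response. Selecting covariates by that criterion has three consequences.

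- A variable unrelated to antibody response enters the model if it happens to differ.
- A variable that does drive response stays out if it happens to balance, although adjusting for it would still gain precision.
- The adjusted model is settled only after the data are seen. As the factors for the multivariate analysis are also unnamed, nothing in the protocol limits the choice.

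The check is also worded as vaccine against placebo, whereas the study's stated aim is to choose between vaccine concentrations and schedules. As written, it need not look at the contrasts between vaccine arms.

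The titre analysis is a separate and smaller matter. A non-parametric test gives a p-value for a shift between groups. It does not by itself say how many times higher titres are in one arm than another, or with what uncertainty.

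**Working it through.** The protocol states no figure here to reproduce. The check covers how often the trigger fires, what it costs, and whether it harms the error rate.

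**Inputs from the protocol.** 136 infants per vaccine group (Sample size considerations). A 5% level is used for the baseline tests; the protocol states p = 0.05 only for Part 1.

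**Inputs that are assumptions.** The number of baseline variables tested (5 to 10), their independence, the correlation r between Day 0 and post-dose log titre, and a true difference of 0.3 SD between arms.

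**1. How often something is significant by chance.** With k independent variables in a two-group contrast, the probability is 1 − 0.95^k.
- k = 5: 1 − 0.774 = 0.226, or 23%
- k = 8: 1 − 0.663 = 0.337, or 34%
- k = 10: 1 − 0.599 = 0.401, or 40%

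This is the chance that some covariate enters the model. It is not an error rate for the vaccine comparison. Any one prognostic variable, by contrast, passes its own test in only about 5% of trials, so the rule would leave it out about 95% of the time.

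**2. Precision available from a pre-named covariate.** ANCOVA multiplies the log-titre variance by 1 − r².
- r = 0.2: 0.96, a 4% reduction
- r = 0.3: 0.91, a 9% reduction
- r = 0.5: 0.75, a 25% reduction
- r = 0.7: 0.51, a 49% reduction

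**3. What the rule recovers of this.** Simulated power with 136 against 136, normal log titres, a difference of 0.3 SD and 5,000 runs per scenario:

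| Analysis | r = 0.3 | r = 0.5 | r = 0.7 |
|---|---|---|---|
| Unadjusted t-test | 70% | 70% | 68% |
| Wilcoxon test | 68% | 68% | 66% |
| Adjust only if baseline p < 0.05 | 70% | 71% | 70% |
| Pre-named ANCOVA | 74% | 81% | 94% |

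The significance rule performs almost like no adjustment at all.

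**4. Type I error of the rule.** With one prognostic covariate it was 4.9%, 4.2% and 3.5% at r = 0.3, 0.5 and 0.7. With 5 or 10 independent variables, one of them prognostic (r = 0.3 or 0.5), and adjustment for every variable reaching p < 0.05, it was 4.1% to 4.7% in 10,000 runs per scenario. There is no inflation; if anything the rule is slightly conservative.

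**The case against.** The strongest reply is that the powered comparison is already fixed. Sample size rests on take rates (70% against 85%, 75% against 87%), and the Data Analysis section assigns those proportions a chi-square test and a rate ratio with 95% CI. The multivariate analysis is listed after these. A reader might infer that the primary immunogenicity model is unknown until the data are seen, but the text does not support that. What stays open is the adjusted analysis that accompanies it.

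A reader might also infer that the trigger invalidates the nominal error rate. The simulations above do not show this. They did not cover free choice among several candidate models, so discretion remains a concern without a measured size.

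Nor is it right that the Day 0 titre goes unused. A four-fold rise needs a pre-dose titre, and the unnamed factors could include it. Only the GMT sentence makes no mention of it.

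On titres, a non-parametric test is defensible: with 70% to 87% take, titres may well mix responders with a cluster at the assay limit. Under normality the Wilcoxon test lost only about 2 points of power against the t-test. GMT ratios and ANCOVA are also things an unseen SAP could supply, so this half is the weaker one.

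Finally, the Background speaks of maternally acquired antibody, while the planned assay is anti-rotavirus IgA. The protocol does not say that Day 0 IgA measures maternal antibody, so its prognostic value is plausible but unproven.

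None of this rescues the trigger itself. It is a stated rule, not a gap, and a SAP naming covariates in advance would have to depart from it.

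**Conclusion.** The point holds in limited form. The protocol fixes a poor rule for choosing covariates. The cost is precision given up and an adjusted analysis that is open to choice after the data are seen; validity of the planned chi-square comparison is not in question.

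The 23% to 40% figure assumes 5 to 10 independent variables tested at 5%. The 4% to 25% variance reduction assumes a correlation of 0.2 to 0.5 and would be at or below its low end if most infants have undetectable Day 0 IgA. The power figures further assume normal log titres and a 0.3 SD difference, so they show direction and do not predict this trial.

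The GMT half stands only as this: the stated comparison yields no ratio or interval and no stated adjustment for Day 0 titre. It does not follow that the non-parametric test is wrong.

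**What to change.** In the Data Analysis section:

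- Delete the sentence that ties adjustment to significant baseline differences. Name age at first dose and Day 0 log IgA titre as the covariates of any adjusted analysis in infants, used whatever the baseline table shows. Use the same two in place of the unnamed factors of the multivariate analysis, and describe baseline characteristics by arm without tests.
- Keep the chi-square test and rate ratio with 95% CI for the proportion with at least a four-fold rise. Add one adjusted rate ratio on the same scale with these covariates, for example from Poisson regression with robust standard errors. Logistic regression would give an odds ratio instead of the planned rate ratio.
- Add an ANCOVA of post-dose log titre on the same covariates, reporting GMT ratios with 95% CI. Keep the non-parametric test alongside it, because many titres may lie at the assay limit.

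The cost is a few sentences. Both covariates are already collected, so no visit, sample or subject is added.

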Fourthly, to warrant shelf life of the vaccine, the commercial lots will have a release titer at a high viral concentration, to ensure that at the expiry of the shelf life, the actual titer is at least equal to the titer for which efficacy was determined. The use of the two viral concentrations in the clinical assay will ensure that there is no safety issue for any of the viral concentration.

Research Design and Methods

Describe in detail the methods and procedures that will be used to accomplish the objectives and specific aims of the project. Discuss the alternative methods that are available and justify the use of the method proposed in the study. Justify the scientific validity of the methodological approach (biomedical, social, or environmental) as an investigation tool to achieve the specific aims. Discuss the limitations and difficulties of the proposed procedures and sufficiently justify the use of them. Discuss the ethical issues related to biomedical and social research for employing special procedures, such as invasive procedures in sick children, use of isotopes or any other hazardous materials, or social questionnaires relating to individual privacy. Point out safety procedures to be observed for protection of individuals during any situations or materials that may be injurious to human health. The methodology section should be sufficiently descriptive to allow the reviewers to make valid and unambiguous assessment of the project. (DO NOT EXCEED TEN PAGES, USE CONTINUATION SHEETS).

Experimental design and methods

Study site: The study will be conducted in a suburb of Dhaka in the area of Mirpur, where phase II ETEC vaccine and killed cholera vaccine trials have been undertaken and several other studies are ongoing. The study will be in one section (section 11) of Mirpur which has a population of about 350,000. Average monthly income per family is about US\$60. The study subjects will be recruited through home visits by the locally recruited field workers.

Overview of study

Part 1 (Safety assessment in toddlers)

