- Serum specimens will be collected at each study visit and 4 weeks after the last dose from all subjects only in part 2.
- Data collection will be by conventional paper case report forms (CRF's).

Sample size considerations

During the first phase of the study (immunization of children 2-4 years of age), the outcome of interest is reactogenicity. Even if intussusception were to occur with a relative risk similar to that observed with RRV-TV, we do not expect to observe intussusception with the small numbers included in this Phase I study. We will however use fever as a measure of reactogenicity. Based on previous studies in the USA involving active surveillance, we expect a background rate of 5% of fever (among placebo recipients). With 90 subjects (30 with $10^{5.0}$ ffu, 30 with $10^{6.0}$ ffu and 30 placebo), we will have 80% power ($p=0.05$) to detect a 35% incidence of fever among vaccinated subjects (assuming a background rate of 5% among controls). The same sample size assumptions hold true for the infant study.

For the second part involving both safety and immunogenicity, the primary outcome measure of interest is immunogenicity, although through this and all subsequent studies, reactogenicity will continue to be monitored. With 136 vaccinees in each vaccine group ($10^{5.0}$ 2 doses, $10^{5.0}$ 3 dose, $10^{6.0}$ ffu 2 doses) and 68 subjects receiving placebo, we will be able to detect a difference in take rates of 15% between the two dose levels (70% vs. 85%). The sample size will be sufficient to detect a difference in take rates of 12% (75% vs. 87%) between 2 doses of $10^{5.0}$ ffu and $10^{6.0}$ ffu. We are also assuming that 35% of infants will be exposed to wild type rotavirus during the 8 week study period and our numbers will be sufficient to differentiate a take rate between vaccine responses and background responses. If the proportion among controls is actually lower, and 70% of children have a four-fold rise in serum antibody titer, then the number of subjects required to achieve significance will be lower.

Study Cohort

Numbers of subjects / centres: Field workers will identify children of appropriate age, inform families of the purpose and scope of the study and offer participation. It is planned to vaccinate 10-12 children daily, and first dose of vaccines are expected to be complete within 2 weeks of the start of the study.

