Stool samples, diluted in PBS will be tested for the presence of rotavirus antigen using ELISA (Unicomb et al, 1993; Azim et al., 1999). Stools found to be positive by ELISA will be further characterized by polyacrylamide gel electrophoresis and by reverse-transcriptase-polymerase chain reaction to determine G and P genotype (Unicomb et al., 1999, Gouvea et al., 1990; Gentsch et al., 1992). A sample of the presumptive vaccine strains will be confirmed as vaccine strains at Smith Kline Biologicals using sequencing. Strains of rotavirus will be typed following a scheme described previously (Unicomb et al., 1999). Anti-rotavirus IgA antibody titers will be determined by ELISA using standard methods (Ward, 1989). Serum samples will be available for neutralization assays, though this is not a stated outcome of the study.

Since the ELISA IgA titers are a crucial outcome of the study and since we want to insure that there is agreement between different studies with the vaccine from different countries, but also want to develop our capacity for carrying out a validated assays in Dhaka, we will split the serum samples and have them tested in the laboratory of either [name] or Smith Kline Biologicals where the assay has been validated. [name] has agreed to be a consultant to assist with the standardization of the assay.

Data Safety Monitoring Committee (DSMB)

A committee will be formed including pediatricians to evaluate the reactogenicity data before moving from the older age to the younger age group. The committee will prepare a letter with its recommendations for the file at each stages in the study.

Expected outcomes and timeframe

1. We expect the vaccine to be safe as determined by our adverse event surveillance when given to toddlers and to infants. We expect to detect no cases of intussusception in either group. The vaccine administration may be associated with mild elevations of temperature with a rate significantly higher than control levels, but this mild reactogenicity will not be perceived as clinically important.
2. We expect that most (>70% of infants) will develop a significant increase in serum IgA antirotavirus antibody titer as determined by ELISA and this take rate will be significantly higher than in those receiving the placebo.

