5. We have recalculated the sample size and accordingly changed the design of the protocol. We feel strongly the necessity to test its candidate vaccine at different viral concentration and at different dose schedules. Moreover, there is evidence in the literature of a rather high attack rate of human rotavirus in Bangladesh between 20 to 30% of children that are hospitalized with diarrhea are infected with rotavirus (Albert et al, J Clin Microbiol. 1999; 37:3458-64. Kilgore, et al. Pediatric Infect Dis J 1996, 15:672-7. Haque et al, J Trop Pediatr. 1994 40:351-4). Previous trials conducted with Rotashield in Bangladesh demonstrated that 75% of vaccinees (aged 6-14 weeks) had a 4-fold or greater rise in IgA titer (unpublished result). We have considered this for the calculation of our sample size.

The outcome of this trial in Bangladesh will provide the information necessary to decide the appropriate viral concentration and dose regimen for testing of the HRV vaccine efficacy and safety in the large phase III trial.

With regards to the fevers, the AVANT uncloned P33 89-12 vaccine candidate was shown to be safe in US infants (Bernstein et al, 1998, Bernstein et al, 1999). After administration of the first dose of 10^5 ffu of uncloned P33 89-12, 19 % of the infants had mild fever as compared to 5% of the infants that received the placebo. The Rota-003 trial (Finland study, phase II, double blind, randomized placebo-controlled trial, unpublished) conducted with the GSK cloned RIX4414 candidate vaccine has confirmed the observed safe reactogenicity profile. None of the subjects that received the 10^5 ffu RIX4414 vaccine or placebo had fever after dose 1. Only one of the subjects that received the 10^6 ffu RIX4414 vaccine had fever after dose 1 and one of the subjects that received placebo. It can be concluded that there is no increase in fevers as observed due to the use of a higher viral concentration.

6. An improved study design is outlined in our revised version.

7. For phase II studies, inclusion and exclusion criteria are quite stringent and these have been spelled out clearly (page 16 and 17). **Annex III** (page 46) provides the composition of the vaccine. Any known

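### Chi-square tests and rate ratios alone suit the Part 1 safety aim poorly at 30 per arm: they put no bound on absolute excess risk and cannot support the statement that no safety issue exists at either concentration

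*Protocol*

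**What the plan says.** The Data Analysis section of the protocol states: "Proportion of infants with adverse events will be compared between the different groups (vaccine, placebo, different doses and viral concentrations". Proportions are to be compared by chi-square tests and "rate ratios (95% confidence intervals"; no interval on the absolute difference is named. The sentence names infants, but no other comparison is described for the toddlers, so I read it as covering both parts.

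The Specific Aims make safety and reactogenicity of each concentration versus placebo the primary aim of Part 1 and a secondary aim of Part 2. Under Sample size considerations, Part 1 is sized with 80% power "to detect a 35% incidence of fever among vaccinated subjects (assuming a background rate of 5% among controls". The fourth rationale at the end of the Background says that using two concentrations "will ensure that there is no safety issue for any of the viral concentration".

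**The concern.** A study whose primary aim is safety should end with a statement of how large an excess risk the data rule out. A difference test in small arms does not supply one, because it can easily be non-significant when a real excess is present. A rate ratio does so only on the relative scale, and it does not exist when the placebo arm has no event. Reading it as an absolute excess needs a placebo risk, which here would itself be estimated from one or two events.

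At stake is the safety conclusion that supports the later phase III work. An assurance that there is no safety issue at either concentration is stronger than these methods can deliver at these arm sizes.

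**Working it through.** **Inputs**
- Arms: 30/30/30 in Part 1; 136/136/136/68 in Part 2 (Overview of study).
- Placebo fever 5%; detectable fever 35%; p = 0.05 (Sample size considerations). Sidedness is not stated; I take it as two-sided.
- Fever means rectal temperature above 38°C (Definitions).
- Predecessor vaccine in infants of 10-16 weeks (Table 1), vaccine vs placebo: 38.1-38.5°C 19% vs 5%; 38.6-38.9°C 6% vs 2%; 39.0°C and above 4% vs 1%. If the bands are exclusive, any fever is 19+6+4 = 29% vs 5+2+1 = 8%.
- No dropout is applied.

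**Formula for power.** Sum Bin(x; n1, p1) × Bin(y; n2, p2) over all tables (x, y) that the test rejects at two-sided 0.05.

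**The protocol's own figure first.** 30 vs 30, 35% vs 5%: Fisher or continuity-corrected chi-square 78.8%; uncorrected chi-square 88.0%; normal approximation 84.6%. The stated 80% is reproduced under Fisher.

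**Power for the cited excesses**

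| Comparison | Uncorrected chi-square | Fisher | Continuity-corrected |
|---|---|---|---|
| Part 1, 30 vs 30, 19% vs 5% | 41.5% | 20.6% | 20.6% |
| Part 1, 30 vs 30, 29% vs 8% | 57.5% | 43.1% | 43.1% |
| Part 2, 136 vs 68, 19% vs 5% | 84.1% | 81.0% | 76.2% |
| Part 2, 136 vs 68, 29% vs 8% | 96.3% | 95.7% | 94.6% |
| Part 2, 136 vs 68, 4% vs 1% | 9.4% | 5.0% | 1.1% |

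In Part 1 the excess is therefore missed 58-79% of the time (19% vs 5%) or 43-57% (29% vs 8%).

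**Is chi-square suitable in Part 1?** At 19% vs 5%, expected fevers are 30 × 0.19 + 30 × 0.05 = 5.7 + 1.5 = 7.2. That is 3.6 per arm under the null, below the usual minimum of 5 for the chi-square approximation. This is why the corrected and uncorrected versions differ so much.

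**Chance that the rate ratio does not exist.** P(no placebo event) = (1 − q)^n.
- Part 1: 0.95^30 = 21.5%; 0.92^30 = 8.2%.
- Part 2: 0.95^68 = 3.1%; 0.92^68 = 0.3%; for an event at 1%, such as fever of 39.0°C or above, 0.99^68 = 50.5%.

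**What each measure says for 5/30 vs 1/30.** Fisher p = 0.19.
- Rate ratio: (5/30)/(1/30) = 5.0. SE of its log = √(1/5 − 1/30 + 1/1 − 1/30) = √1.133 = 1.065. The 95% interval is 5.0 × exp(±1.96 × 1.065) = 0.62 to 40.3.
- Risk difference: 16.7 − 3.3 = 13.3 points. The Miettinen-Nurminen limits are the values δ at which (p1 − p2 − δ) / √{[p̃1(1 − p̃1)/n1 + p̃2(1 − p̃2)/n2] × N/(N − 1)} equals ±1.96, with p̃1 − p̃2 = δ. Result: −2.5 to 31.0 points. Newcombe gives −2.9 to 30.5.

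**With no events at all (0/30 vs 0/30).** There is no rate ratio. The Newcombe upper limit equals the Wilson limit z²/(n + z²) = 3.84/33.84 = 11.4 points.

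**Part 2, 5/136 vs 1/68.** Fisher p = 0.67; rate ratio 2.5 (0.30 to 21.0); risk difference 2.2 points (Miettinen-Nurminen −4.5 to 7.1).

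**The case against.** Much of the opposing case stands.

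- **No rule equates non-significance with safety.** A reader might infer that p > 0.05 will be reported as safe. The documents do not say so. Expected outcomes and timeframe speaks of safety as judged from adverse event surveillance. The step to Part 2 rests on a blinded review by the medical monitor and on the DSMB's judgement, not on a test between arms.
- **Harm is not wholly unbounded.** The planned 95% intervals on the rate ratio bound relative harm whenever they can be computed. What is missing is an absolute bound.
- **The cited excess is borrowed.** It comes from infants given the predecessor vaccine. Table 1's row for 2-12 years shows no fever in either group, and the reply to external reviewers reports almost none with RIX4414 in another trial. The figures illustrate sensitivity; they do not predict fever in toddlers.
- **Undefined rate ratios are not common throughout.** The problem is confined to Part 1 and to rare events. For any fever in Part 2 the chance is about 3% or less.
- **Low sensitivity is disclosed.** The protocol says openly that Part 1 is sized for 35% vs 5%.
- **The mild-fever remark is not a decision rule.** One might read "but this mild reactogenicity will not be perceived as clinically important" as making every result count as safe. It is a stated expectation about mild temperature rises only. Nor does the reply to external reviewers about fever in another trial form part of this trial's analysis.

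An acceptable margin and the handling of zero cells may properly sit in a statistical analysis plan or DSMB charter that is not shown. Their absence is not held against the protocol. The choice of effect measure, however, is fixed in the protocol, and so is the background assurance.

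**Conclusion.** The concern holds in a limited form. The effect measure fixed in Data Analysis is a poor fit for the primary aim of Part 1. It is undefined in about 21% of trials at 5% placebo fever (8% at a placebo rate of 8%) and gives no absolute bound when it is defined. The accompanying test would miss the predecessor's infant fever excess 58-79% or 43-57% of the time, depending on whether one band or all bands are counted. In Part 2 the weakness is limited to rare events: at 4% vs 1% power is at most about 9%, whereas 19% vs 5% has about 81-84% power by Fisher or uncorrected chi-square (76% with continuity correction).

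The assurance in the Background is therefore stronger than the planned analysis can support. The sample size statement is not in error.

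These figures assume two-sided 0.05, no dropout and one vaccine arm against placebo. The 29% vs 8% figures also assume that Table 1's bands are exclusive.

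**What to change.** 1. In Data Analysis, for each concentration versus placebo and for 10^6 versus 10^5 ffu, make the risk difference with a score-type 95% interval (Miettinen-Nurminen or Newcombe) the lead measure. Keep the rate ratio as secondary.
2. Use an exact test where counts are small, as they will be in Part 1.
3. State that safety conclusions are read from the upper limit of the risk difference.
4. Reword the fourth rationale in the Background so that the study is said to bound the excess risk at each concentration.

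This changes analysis and wording only, with no added children, visits or tests. The price is a less favourable safety statement, because Part 1 can exclude only large excesses: about 11 points with no events in either arm, and about 31 points at 5/30 vs 1/30.
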